5.1.2 Other Evaluations, Measures

Subjects and caregivers will complete the following measures:

| Table 1. Study Measures. | | Baseline | Day +5 | Day +10 | Day +15 |
|--------------------------|--|----------|--------|---------|---------|
| Construct | Measure | | | | |
| Acceptability | Patient, caregiver, and nurse will respond to a brief questionnaire of acceptability of adjusting vitals checks. | | | | x |
| Demographics | Report of sex, race/ethnicity, age of child and caregiver | x | | | |
| COVID-19 Impact | COVID-19 Exposure and Family Impact Survey (CEFIS) to assess family exposure to and experience with COVID-19 through Yes/No responses (25 items); 12 items assessing the impact of the pandemic on | x | | | |

| | | | | | |
|---------------------------|---|---|---|---|---|
| | self/family with 1-4 intensity scale and 1 open-ended item | | | | |
| HRQL and related symptoms | Pediatric Quality of Life Inventory—Stem Cell Transplant Module. This measure assesses HRQL and symptoms relevant to patients undergoing HSCT. The measure includes questions about pain, fatigue/sleep, nausea, communication, worry, nutrition, thinking and other symptoms answered on parallel child and adolescent with parent proxy forms (41 items). ²⁶ | x | x | x | x |
| Sleep | PROMIS Sleep Measures—Sleep disturbance, sleep-related impairment, and sleep hygiene over the past week-parallel parent/child forms (24 items) ²⁷ . | x | x | x | x |
| Supportive Care Use | EHR review to document engagement or refusal of PT/OT/School/Creative Art Therapy/ Psychology for each 5 day period. | | x | x | x |
| Actigraphy | Worn by participant day 0-night of Day +14, removing on awakening on Day+15. To validate actigraphy: bedtime, waketime, night awakenings, naps, time actigraph was off reported daily through text messages delivered via REDCap and its integration with Twilio. | | | | |

5.2 Efficacy Evaluations

5.2.1 Diagnostic Tests, Scales, Measures, etc.

Actigraphy will be used to track the impact of extending vitals check on sleep.

5.3 Safety Evaluation

Subject safety will be monitored by adverse events, study visits, and daily checks with the subject's treatment team during the intervention (i.e., extended vitals checks) period.

6 STATISTICAL CONSIDERATIONS

6.1 Primary Endpoint

The primary endpoint is the acceptability and feasibility of the intervention. Acceptability will be measured by subjects, caregivers, and nursing ratings of the intervention. Feasibility will be measured through study staff documented medical eligibility to participate in the intervention each eligible day and by tracking compliance with extended vitals checks, through electronic health record (EHR) review.

6.2 Secondary Endpoints

Secondary endpoints will include the following:

- The change in sleep between observation and intervention period as measured by actigraphy sleep efficiency, total sleep time, and number of awakenings.
- The change in engagement in supportive services between observation and intervention period (physical therapy, occupational therapy, school and/or psychology) as measured through EHR review.

6.3 Statistical Methods

6.3.1 Baseline Data

Baseline and demographic characteristics will be summarized by standard descriptive summaries (e.g. means and standard deviations for continuous variables such as age and percentages for categorical variables such as gender).

6.3.2 Efficacy Analysis

Using descriptive statistics, feasibility will be determined by assessing medical eligibility for the intervention and the delivery of the intervention. Descriptive statistics will be used to characterize acceptability measure responses

Secondary endpoints will include the change in sleep parameters and engagement in supportive care services. We will utilize hierarchical multilevel mixed-effects models for daily diary data, which uses all available data, allows for multilevel nesting (e.g., daily data nested within participants, nested within condition), and are fairly robust to missing data (models are valid under Missing At Random assumption)²⁸. Fixed and random effects models will be fit to the data²⁹ to estimate the impact of the intervention on nocturnal sleep (sleep efficiency, total sleep time, night awakenings); Aim 2) and engagement in supportive care, HRQL, and symptom burden (Aim 3). We will test for carryover effects of the intervention and adjust analyses as needed²⁹.

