3.1.2 Study Treatment Phase (start of the study intervention)

One-two days before the transplant, a study team member will meet with the family to complete the informed consent, baseline measures, and give actigraphy instructions. All patients will wear an actigraph from the day of the transplant until day +5 from the transplant to serve as the “observation baseline” for each patient.

3.1.3 Phase 2

On Day +5, to reduce the impact of expectancies during the first observation period, patients will be randomized to ABA (observation/intervention/observation) or AAB (observation/observation/intervention), with each period lasting 5 days (Fig. 1). Block randomization stratified by age will be used to ensure similar age distribution between groups. The two group design will allow for the comparison of altering vitals checks before/after engraftment and peak symptom burden (typically on day +10⁴). On each intervention night, the research team will verify with the child's provider that it is acceptable for the patient to have a 6-hour window between vitals checks. This confirmation will be communicated to the child's nighttime nurse. For the 5 days of the child's intervention period, the nurse will be instructed to conduct the last vitals check between 9pm-1am. After the last vitals check, the patient will be given 6 hours until the next vitals check, unless the caregiver/patient request nursing. Patients will continue to wear the actigraph until the end of the study. The patient can remove the actigraph upon awakening on Day +15.

Eligibility for extended vitals check, assessed daily: 1) No fever in the last 24 hours; 2) No concurrent chemotherapy administration; 3) No ongoing or active infection; and 4) No organ toxicity requiring labs more than every 6 hours. Even if a patient is ineligible for extended vitals checks they are asked to continue to wear the actigraph.

After each patient has completed both the intervention and a second observation (either BA or AB), they will be asked to complete final study measures and measures of acceptability of the intervention.

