3.2 Allocation to Treatment Groups and Blinding

Participants will be randomized to either Observation/Intervention or Intervention/Observation on day +5 post-transplant. The research coordinator will generate a randomization sequence using a random number generator, with block randomization occurring based on participant age (8-12 or 13-21). Blinding will not be possible, but randomization will occur on day +5 to minimize the impact of the intervention on the initial observation period.

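### Section 6.3.2 names no period term and leaves the role of days 0 to +4 open, so one permitted analysis would bias the secondary effect sizes; its test-then-adjust carryover rule is weak

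*Combined protocol and SAP*

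**What the plan says.** Section 6.3.2 is the whole inferential plan for the secondary outcomes. It proposes mixed-effects models on all available data, "to estimate the impact of the intervention on nocturnal sleep (sleep efficiency, total sleep time, night awakenings", and likewise for "engagement in supportive care, HRQL, and symptom burden (Aim 3". The only levels it mentions are day, participant and condition; the approach "allows for multilevel nesting (e.g., daily data nested within participants, nested within condition". It names no period, day or time-since-transplant term. On carryover it says "We will test for carryover effects of the intervention and adjust analyses as needed", with no test level and no form of adjustment.

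On the design, Section 3.1.3 says "patients will be randomized to ABA (observation/intervention/observation) or AAB (observation/observation/intervention", with five days per period. Days 0 to +4 are therefore observation in both sequences, and only the order of periods 2 and 3 is randomised. Sections 3.2 and 9.1.1 describe two periods: "Participants will be randomized to either Observation/Intervention or Intervention/Observation on day +5 post-transplant". Section 3.1.2 says "All patients will wear an actigraph from the day of the transplant until day +5 from the transplant to serve as the" observation baseline. Sections 2.2 and 6.2 compare observation with intervention without saying which observation days are meant. Section 3.1.3 adds that "The two group design will allow for the comparison of altering vitals checks before/after engraftment and peak symptom burden", the peak being typically at day +10.

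On time trends, Section 1.3 reports that sleep, measured by one global question, worsens from one week before transplant to three weeks after. Sections 1.1 and 1.3 put the peak of symptom burden at about day +10. Section 6.4 justifies the sample by the need to estimate effect sizes for a future trial.

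**The concern.** Nobody receives the intervention in period 1. If all observation days are pooled and compared with intervention days, condition partly stands for time since transplant, and any change after day +4 is credited to the intervention. The protocol's own background expects such change. Worsening sleep would hide a real benefit, and rising symptom burden would make the intervention look harmful. Two analysts following Section 6.3.2 could report different effects, and the future trial could be sized on the wrong one.

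The carryover rule has a separate problem. The main estimate depends on the result of a test with little power, and the nominal error rate is not kept. A positive result is also ambiguous, because carryover and a difference between early and late intervention appear in the same contrast.

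**Working it through.** The plan gives no SD, effect size or alpha for these models, so it has no figure of its own to reproduce.

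**Inputs from the documents:** ABA/AAB sequences and five nights per period (3.1.3); n=16 (6.4) and n=50 evaluable (3.3.2). These two sample sizes differ, so both are used.

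**Assumed inputs:** 1:1 allocation, complete data, two-sided 5%, night-to-night SD 75 min, between-patient SD 40 min, participant-by-period SD 25 min.

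**1. Bias with all periods and condition only.** Let P1, P2, P3 be the period means without intervention.
- ABA contributes P2 - (P1+P3)/2 and AAB contributes P3 - (P1+P2)/2.
- Their average is 1/2 x [(P2+P3)/2 - P1]. It does not contain n.
- A fall of 15, 30 or 45 min after period 1 gives -7.5, -15 or -22.5 min.
- A linear trend, with period midpoints at days 2, 7 and 12, gives 1/2 x (9.5 - 2) = 3.75 x the daily slope.
- Suppose symptom burden rises and falls by s points per day around day +10. Values at days +5, +10 and +15 give 1/2 x (-2.5 + 5)s = +1.25s. Period midpoints give 1/2 x (-2.5 + 8)s = +2.75s.

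**2. Periods 2 and 3 only.** With share p in ABA, the bias is (2p - 1)(P2 - P3). This is zero at p = 1/2. At 9/7 it is 0.125 x (P2 - P3), and at 27/23 it is 0.08 x (P2 - P3).

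**3. Categorical period term.** Bias is zero with or without days 0 to +4, at 8/8, 9/7, 25/25 and 27/23. With balanced, complete data period 1 has zero weight. A single linear day term is not enough: for period means 0, -0.4, -0.4 SD it leaves about -0.08 to -0.09 SD.

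**4. Standard errors.** Excluding the patient effect, a period mean has variance 25² + 75²/5 = 1750 (SD 41.8).
- Condition only, three periods: sqrt(1.5/n) x 41.8 = 12.8 (n=16) and 7.2 (n=50).
- With the period term: sqrt(2/n) x 41.8 = 14.8 and 8.4. The ratio is sqrt(4/3) = 1.155.
- Periods 2 and 3 only: the same as with the period term.
- A bias of -15 min is thus about 1.2 SE at n=16 (15/12.8) and 2.1 SE at n=50 (15/7.2).

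**5. What the carryover contrast estimates.** Let d be ABA minus AAB within a period; d1 has expectation zero.
- Constant effect T and carryover L into period 3: d2 = T and d3 = L - T, so d2 + d3 = L.
- No carryover, early effect E and late effect F: d2 = E and d3 = -F, so d2 + d3 = E - F.
- The main estimate (d2 - d3)/2 equals T - L/2 when carryover is present.

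**6. Power of the carryover test with a random participant effect.**
- The variance is (4/n) x [2(1750) + 4(1600) - 3200²/3350] = (4/n) x 6843, so the SE is 41.4 (n=16) or 23.4 (n=50).
- For L = 30 min, 30/41.4 = 0.73 gives 11% power and 30/23.4 = 1.28 gives 25%.
- With no participant-by-period variation the figures are 14% and 33%.

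**7. Type I error of test-then-adjust.**
- The adjusted estimate is the main estimate plus half the estimated carryover. At n=16 its SE is sqrt(14.8² + 41.4²/4) = 25.4.
- After a positive pretest it contains half of a quantity just selected for being large. By simulation with no effect and no carryover, it then rejects about 46% of the time (5% pretest) or 32.7% (10% pretest).
- Overall: 0.95 x 5% + 5% x 46% = about 7.0%; 0.90 x 5% + 10% x 32.7% = 7.7 to 7.8%. Neither depends on n.

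**The case against.** The strongest reply is that silence is not a flaw. Bias needs three things together: days 0 to +4 in the contrast, no period term, and a time trend. A reader might infer that the planned estimates are biased, but the documents do not support that. Section 6.3.2 does not exclude a period term, and including days 0 to +4 with such a term is unbiased. Sections 3.2 and 9.1.1, and the baseline role given to days 0 to +4 in Section 3.1.2, lean towards a contrast of periods 2 and 3. The evidence for pooling is wording only: the shared letter A in ABA/AAB, the plural observation periods in the abstract's objective, and the use of all available data. The methods paper on aggregated N-of-1 trials cited beside the model and carryover sentences may also say more. All of this stands. It limits the point to an open choice with one harmful branch; a citation still does not say which terms this trial will fit.

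The magnitudes are assumed, and the only sleep trend in the documents comes from one self-report question rather than actigraphy. That also stands, although the direction and the formula do not depend on the SDs.

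A reader might infer that carryover cannot be estimated at all. It can be, within patients, if the effect is the same early and late. The faults are low power, the two-stage rule and the ambiguity with timing. Nothing here rests on the nesting phrase, which is only an example of what such models allow.

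**Conclusion.** The point holds as an under-specified analysis with one biased branch, not as a demonstrated bias. On that branch the error is 1/2 x [mean(P2,P3) - P1] at any sample size: -15 min for an assumed 30-min fall in sleep, and an apparent increase in symptom burden if it peaks near day +10. On the periods 2 and 3 branch there is no bias at 1:1 with complete data.

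The carryover rule is weak under every assumption tried: 11 to 14% power at n=16 and 25 to 33% at n=50 for a 30-min period-level carryover, and overall type I error above the nominal 5%. These figures rest on the assumed SDs.

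The descriptive feasibility and acceptability analysis is untouched. The point should still be fixed, because the secondary models supply the effect sizes that Section 6.4 wants for the next trial.

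**What to change.** In Section 6.3.2:
- Fit fixed effects for condition, categorical period (days 0 to +4, +5 to +9, +10 to +14) and age stratum, with a random participant effect. For nightly outcomes add a random participant-by-period effect; if that variation exists at SD 25 min and is left out, false positives are about 10% rather than 5%.
- State the role of days 0 to +4. Their zero weight holds exactly only in balanced, complete data.
- Use the pre-transplant questionnaire value, where collected, as a baseline covariate or a separate time level.
- State that nights are analysed by assigned condition, including nights when the patient was ineligible for extended vitals checks.
- Base the main estimate on this model whatever a carryover test shows. Report a carryover-adjusted model only as a fixed sensitivity analysis, and state that the early-versus-late comparison assumes no period-level carryover.

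The cost is analysis wording only, with no new data. The SE is about 15% higher than in a condition-only three-period model; if there were no trend, power for an assumed +20 min would fall from 33% to 26% (n=16) or from 78% to 66% (n=50). Against a periods 2 and 3 contrast the period term costs nothing. One limitation remains: an undetected period-level carryover of L biases the main estimate by -L/2, for example -15 min for L = 30.

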6.3.3 Safety Analysis

AE incidence will be summarized along with the corresponding exact binomial 95% two-sided confidence intervals.

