8 SAFETY MANAGEMENT

8.1 Clinical Adverse Events

Clinical adverse events (AEs) will be monitored throughout the study.

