8.2 Adverse Event Reporting

Since the study procedures are not greater than minimal risk, SAEs are not expected. If any unanticipated problems related to the research involving risks to subjects or others happen during the course of this study (including SAEs) they will be reported to the IRB in accordance with CHOP IRB SOP 408: Unanticipated Problems Involving Risks to Subjects. AEs that are not serious but that are notable and could involve risks to subjects will be summarized in narrative or other format and submitted to the IRB at the time of continuing review.

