9.4 Regulatory and Ethical Considerations

9.4.1 Data and Safety Monitoring Plan

An independent Data Safety and Monitoring Board will not be instituted due to the low degree of risk with this study. The PI will oversee all data collection through the implementation of standardized data collection procedures. Safety monitoring will include careful assessment and appropriate reporting of AEs as indicated below, and will also include a regular assessment of the number and type of serious AEs. Any serious AEs that might reasonably be due to the study will be reported to the CHOP IRB within 24 hours of its occurrence. Events that are not related to the study but classified as imminent risk to the subjects will be reported to the investigators and appropriate clinical referrals will be made.

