9.4.2 Risk Assessment

The risks associated with this study are minimal and generally not in excess of those encountered in the hospital stay. Specifically, risks include: 1) breach of confidentiality; 2) discomfort from questions regarding cancer history and current symptoms; 3) inconvenience of study procedures. Because participants are assessed on a daily basis for whether they are medically able to participate in extended vitals checks, the medical risk for extending time between vitals checks by 2 hours is assumed minimal. If a participant develops a fever during the extended vitals checks portion of the study, there is a risk that it will not be detected for an additional 2 hours. All participants can contact their nurse at any time between vitals checks for usual care or concerns such as fever. All participants will be informed of these risks prior to participation and will be informed of the right to discontinue participation if they are uncomfortable with the study. If participants become upset, [name] (licensed clinical psychologist, Director of Psychosocial Services in Oncology at CHOP) will assess the level of distress of the patient and determine the need for additional psychosocial support.

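### The safety analysis specifies no split of adverse events by condition, and daily team checks are stated for the intervention period only, so the plan as written gives little information on whether longer gaps between vitals checks add harm

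*Combined protocol and SAP*

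**What the plan says.** Section 6.3.3 is the complete safety analysis: "AE incidence will be summarized along with the corresponding exact binomial 95% two-sided confidence intervals". It does not say whether incidence is per child or per night, over which days, or under which condition.

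On how events are found, section 8.1 says "Clinical adverse events (AEs) will be monitored throughout the study" but gives no method. Section 5.3 lists three sources: adverse events, study visits, and "daily checks with the subject's treatment team during the intervention (i.e., extended vitals checks) period". Only the third is tied to a condition. The chart-abstraction list in 5.1.1 includes the timing of vitals checks for each study day but has no AE or fever item.

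The other safety passages add no comparison. Section 9.4.1 says monitoring "will also include a regular assessment of the number and type of serious AEs". Section 8.2 says "AEs that are not serious but that are notable and could involve risks to subjects will be summarized in narrative or other format". Neither is split by condition.

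Section 9.4.2 names a harm specific to the intervention. If a child becomes febrile during an extended gap, "there is a risk that it will not be detected for an additional 2 hours".

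By contrast, section 6.3.2 plans mixed models for the intervention's effect on sleep, supportive care, HRQL and symptom burden.

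**The concern.** Each child is observed under both conditions, and the order over Days +5 to +14 is randomised. The plan uses that within-child contrast for the hoped-for benefits but specifies no use of it for harm. The subjects are transplant inpatients, in whom adverse events will be common whatever the vitals schedule. An incidence taken over the whole stay mostly describes that background.

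At stake is what the pilot can hand on. Section 2 says it will provide evidence for a clinical intervention, there is no independent monitoring board (9.4.1), and the medical risk of the longer gap is assumed minimal (9.4.2). As written, no planned summary bears on that assumption. If someone later splits the events by condition, the stated difference in daily checks leaves open whether an excess in the intervention period reflects more events or closer looking.

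**Working it through.** The plan states no safety rate, precision or power, so there is no figure to reproduce. All AE rates below are assumptions, shown as ranges.

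**Inputs from the documents.** There are three 5-day periods per child, ordered ABA or AAB (3.1.3), so 10 observation days and at most 5 extended days. Five is a maximum because eligibility for the extended check is assessed daily. N is 16 (6.4) or 50 evaluable (3.3.2). The interval method is exact binomial, two-sided 95% (6.3.3).

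**1. How far an unsplit incidence moves.** Let p be the daily AE risk, doubled on all five intervention days. Days are taken as independent.

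- No added harm: 1 − (1 − p)^15
- Doubled risk: 1 − (1 − p)^10 × (1 − 2p)^5

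| p | No added harm | Doubled on 5 days |
|---|---|---|
| 0.01 | 14.0% | 18.3% |
| 0.02 | 26.1% | 33.4% |
| 0.05 | 53.7% | 64.6% |
| 0.10 | 79.4% | 88.6% |
| 0.20 | 96.5% | 99.2% |

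For p = 0.05: 1 − 0.95^15 = 0.537, and 1 − 0.95^10 × 0.90^5 = 1 − 0.599 × 0.590 = 0.646. If only three of the five nights are extended, the second figure is 1 − 0.95^12 × 0.90^3 = 0.606.

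**2. Whether the planned interval could show the shift.** With 50 children, 27/50 (54%) has an exact 95% interval of 39% to 68%, and 32/50 (64%) has 49% to 77%. At p = 0.02, the interval for 15/50 (30%) is 18% to 45%, which covers both 26.1% and 33.4%. A single-group interval also has no reference value: the reader would not know what incidence to expect without the intervention.

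**3. The same doubling, split by condition.** Five-day risk is 1 − (1 − p)^5 against 1 − (1 − 2p)^5. At p = 0.02 this is 9.6% against 18.5%. At p = 0.05 it is 22.6% against 41.0%. The contrast is no longer diluted by ten observation days.

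**4. What unequal ascertainment could do to a later split.** Suppose true risks are equal and 90% of events are captured in the intervention period. Capture of 75%, 60% or 50% in the observation period gives apparent risk ratios of 0.90/0.75 = 1.2, 0.90/0.60 = 1.5 and 0.90/0.50 = 1.8. These capture rates are illustrative; the documents give none.

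**5. How much a corrected analysis could show.** Exact McNemar power, two-sided 0.05, periods independent within child:

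| Five-day risk, observation vs intervention | N = 16 | N = 50 |
|---|---|---|
| 10% vs 20% | 0.02 | 0.20 |
| 20% vs 30% | 0.03 | 0.15 |
| 20% vs 40% | 0.11 | 0.50 |
| 10% vs 30% | 0.11 | 0.63 |

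If no child has an event in the intervention period, the exact 95% upper limit is 20.6% at N = 16 and 7.1% at N = 50. The corrected analysis is therefore descriptive at either sample size.

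**The case against.** The strongest reply is that this is a minimal-risk pilot whose primary aim is acceptability and feasibility. Comparative safety is not among its objectives, so a powered comparison of harm should not be expected. That stands, and it limits the remedy to a descriptive one. It does not explain why the plan specifies no tabulation by condition at all.

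Three stronger readings are tempting, and the documents do not support them.

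- A reader might infer that the plan rules out a split, or that the trial can never compare safety. Section 6.3.3 is silent; it does not commit to one pooled figure. Events are monitored throughout (8.1) and periods are fixed by day, so a split would be possible if onset dates are kept.
- A reader might infer that ascertainment is certainly biased. Two of the three sources in 5.3 are not tied to a condition, and all subjects are inpatients throughout. The nightly contact described in 3.1.3 and 7.1 confirms that the extended window is acceptable; neither section calls it a search for adverse events. Bias is possible, not shown.
- A reader might count nights and conclude that a split would detect harm readily. With 250 nights per condition at 10% against 20%, z = 0.10/√((0.09 + 0.16)/250) = 3.2. That needs 50 children, every intervention night delivered, independent nights and rates found nowhere in the documents. With the 16 subjects of 6.4 (80 nights per condition), z is 1.8, or about 1.3 with a design effect of 2.

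It is also fair to say that AE counts may miss the named harm: a fever detected late is still one fever. Counts by condition are necessary context, not a measure of delay.

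**Conclusion.** The concern holds in a limited form. The plan specifies no AE summary by condition, and its one stated daily safety contact is tied to the intervention period. Followed as written, the 15-day incidence responds weakly to added harm (54% to 65% at an assumed daily risk of 0.05 with all five nights extended, less with fewer), and a later split could be biased in either direction. Extra checks would push the intervention count up. Restricting extended checks to nights without recent fever or active infection would push the count on delivered nights down.

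The dilution appears at every rate tried; its exact size rests on the assumed rates, independence between days and a doubling of risk. Correcting the plan would give an interpretable descriptive contrast, not a test of harm. The change should be made before the data are analysed, because unequal ascertainment cannot be repaired afterwards.

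**What to change.** **Section 6.3.3.**
- Tabulate AEs, with onset dates, by randomised condition for Days +5 to +14: children with at least one AE, and AEs per patient-night.
- Give exact 95% intervals for the per-child proportions and a descriptive within-child contrast adjusted for period.
- Report Days 0 to +4 separately, since that period is always observation and is not randomised.
- Add a supportive table by nights on which the extended check was actually delivered, noting that such nights are selected by the daily eligibility assessment.
- State that the comparison is descriptive and cannot exclude harm.

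**Sections 5.3 and 5.1.1.** Ascertain AEs the same way on all nights of Days +5 to +14. Alternatively, restrict the comparison to AEs abstracted identically from the EHR, and add AE onset, including fever, to the abstraction list.

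**Sections 6.4 and 3.3.2.** Reconcile 16 subjects with 50 evaluable, so that the safety denominator is defined.

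**Cost.** One more table and one added abstraction item, or a brief extra check on five more days per child. No clinical rule needs to change.
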